9.2 PROPOSED ANALYSES

All statistical analyses will be pre-specified in a comprehensive statistical analysis plan agreed prior to database lock. The plan will be authored by the study statistician and agreed by the independent study oversight committees.

The primary outcome will be analysed using a ranking process for each of its components i.e., they will be ranked according to the possible outcomes at 30 days (1 best: 6 worst) according to severity/importance:

[1] No death, no MACE, no new MINS

[2] No death, no MACE, but new MINS

[3] No Death ≥1 MACE

[4] Death, no MACE, no new MINS

- [5] Death, plus new MINS
- [6] Death plus ≥1 MACE

These ranks will form the basis of the primary analysis using the Wilcoxon-Mann-Whitney rank sum test, under an intention to treat principle, as appropriate for a superiority design. We will also consider a potentially more powerful analysis using Koch's non-parametric ANCOVA, adjusting for the stratification variables included in the randomisation i.e., centre, age (<80 vs. \geq 80 years) and pre-existing CVD. If appropriate, analyses will be adjusted for site as a random effect. On review of baseline characteristics, the extent of the association between pre-existing CVD and anticoagulant use will be assessed and, if it is found that anticoagulant use is not strongly associated with pre-existing CVD, then it will be included as an additional covariate in all adjusted analyses. As a secondary analysis, we will assess the primary outcome using an ordinal logistic mixed effects regression. We will explore the robustness of the findings to any missing data using multiple imputation according to Rubin's approach under an assumption of

CR007-T02 v0.5 Page **42** of **69**

IRAS 299977/308830

Version 5.0 26Jun2024

missing at random. We do not expect the level of missing data to be high, and hopefully less than the assumed 10%, making an approach assuming informative missing-ness unlikely to be either necessary or feasible.

To address the possibility that any component of the primary outcome (particularly Atrial fibrillation (AF) or new MINS) is much more prevalent in the trial than expected and dominates the primary composite outcome, we propose the following: all the individual components of MACE and new MINS will be reported as secondary outcomes and an a priori sensitivity analysis is undertaken with the AF and new MINS components of the primary outcome removed. This will be pre-specified in the statistical analysis plan when developed and proposed as a secondary analysis.

Secondary outcomes will be analysed using logistic regression for binary outcomes and linear regression for normally distributed continuous outcomes. Continuous outcomes that are not normally distributed will be analysed using appropriate non-parametric techniques. Time to event data will be analysed using an appropriate survival model (e.g., Cox proportional hazards).

Pre-specified sub-group analyses will explore effects in relation to gender, age (<80 vs. \geq 80 years), presence of pre-existing CVD and use of anticoagulant and antiplatelet drugs. These will be analysed as per the primary outcome but including a covariate*treatment interaction.

No interim analysis is planned.

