3.4 INCLUSION AND RANDOMISATION CRITERIA

Inclusion Criteria

- Adults aged 60 years or over
- Admitted to acute hospital unit for operative management of hip fracture

Randomisation Criteria

• Presence of anaemia (Haemoglobin equal to or less than 90 g.L⁻¹) at any time from admission until the seven days following surgery

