4.3 RANDOMISATION

Participants should be randomised as soon as possible after the triggering haemoglobin measurement and no later than post-operative day 8.

Participants will be randomised by remote computer to ensure allocation concealment. Allocation will be in a 1:1 ratio with stratification by centre, age (<80 vs. \geq 80 years) and preexisting diagnosis of cardiovascular disease. Randomisation will be performed using a webbased randomisation system developed by the Edinburgh Clinical Trials Unit (ECTU).

Due to the nature of the intervention blinding of trial participants and local study teams will not be possible, however the primary outcome assessment will be adjudicated by a panel blinded to treatment allocation.

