8 DATA MANAGEMENT

8.1 PERSONAL DATA

[figure not shown]
The following personal data will be collected as part of the research:

- Participant name, address, telephone number and participant representative details (if appropriate), will be recorded on a contact details CRF and stored securely within the ECTU study database to facilitate central follow up by the research team at each site. Access to contact details data will be minimised and only accessible to those with delegated responsibility. Personal data will be stored for a minimum of 5 years after the study end date.
- Patient initials will be recorded on screening logs and stored securely within the ECTU REDCAP database for the purpose of monitoring and reporting patient flow through the trial via the production of a CONSORT diagram.
- Patient gender, date of birth and National Health Service (NHS) number, hospital number, Community Health Index (CHI) number, or other unique hospital identifier will be recorded and stored securely within the ECTU REDCAP database for the purposes of statistical analysis and correct identification of patients by research teams for follow up.
- Personal data will be stored at site by research teams on NHS computers (desktop and laptop). Computers will be password protected and kept in locked offices. All paper files containing personal data will be held in a secure location according to local NHS/University policies, as applicable.
- Personal data entered onto the ECTU REDCAP database will be hosted securely on University of Edinburgh servers. Only approved delegated members of the local research team or wider study team will have access to personal data.

Baseline and follow up data to 120 days, including de-identified scans of ECG's and other cardiac investigations e.g. angiogram, will be collected by the local research team at each site and entered onto /uploaded to the ECTU REDCAP database. The local research team can only view the records of patients from their own centre.

IRAS 299977/308830

Version 5.0 26Jun2024

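### Age enters the adjusted analysis and the age interaction in section 9.2 only as below 80 versus 80 or over, although exact age is held: valid, but mildly inefficient, and free to improve

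*Protocol*

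**What the plan says.** Section 4.3 stratifies the randomisation by age: "Allocation will be in a 1:1 ratio with stratification by centre, age (<80 vs" 80 and over), together with pre-existing cardiovascular disease. Section 3.4 admits "Adults aged 60 years or over", with no upper limit.

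Section 9.2 uses age in three different ways:

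- **Primary analysis: no age term.** "These ranks will form the basis of the primary analysis using the Wilcoxon-Mann-Whitney rank sum test".
- **Adjusted analysis: two levels.** "We will also consider a potentially more powerful analysis using" Koch's method, "adjusting for the stratification variables included in the randomisation i.e., centre, age (<80 vs" 80 or over) and pre-existing cardiovascular disease.
- **Age subgroup: two levels.** "Pre-specified sub-group analyses will explore effects in relation to gender, age (<80 vs" 80 or over), among other factors. "These will be analysed as per the primary outcome but including a covariate*treatment interaction".

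Section 9.2 also plans an ordinal mixed model and regressions for the secondary outcomes, but gives no covariate list for them.

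Exact age is available. Section 7.1 lists date of birth at enrolment and age at randomisation. Section 8.1 says that "Patient gender, date of birth and National Health Service (NHS) number" and other identifiers are stored, with statistical analysis among the stated purposes.

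**The concern.** A cut-point is needed to form randomisation strata, but not in a model. With two levels, participants aged 61 and 79 are treated as identical, and the whole age effect becomes a step at 80. Section 9.2 wants the adjusted analysis because it may be more powerful, so using the coarser form of a covariate already in the database works against that aim.

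Two quantities are at stake. One is the precision of the adjusted treatment effect. The other is the power of the prespecified test of whether the effect of a liberal strategy varies with age. They respond very differently, so they are sized separately below.

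**Working it through.** The protocol states no figure for age information or for interaction power, so there is nothing to reproduce first. It also gives no mean age, standard deviation or share aged 80 or over. The age distributions below are assumptions.

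**1. Share of age variance kept by the split.** This is the squared correlation r² between age and the indicator of age ≥80. For a normal covariate, r² = φ(c)²/(p(1−p)), where p is the share above the cut. At p = 0.5 it is 2/π = 0.637, a loss of 36%. For normal age truncated at 60 and 105, by numerical integration:

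| Mean/SD | Share ≥80 | r² | Loss |
|---|---|---|---|
| 80/9 | 0.51 | 0.655 | 35% |
| 82/8 | 0.60 | 0.631 | 37% |
| 83/8 | 0.65 | 0.614 | 39% |
| 84/8 | 0.69 | 0.592 | 41% |
| 85/7 | 0.76 | 0.534 | 47% |

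For a uniform spread from 60 to 100, the covariance is 0.5 × 10 = 5 and the variance is 40²/12 = 133.3. So r² = 25/(133.3 × 0.25) = 0.75, a loss of 25%.

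**2. Adjusted treatment effect.** If exact age explains a share R² of outcome variance, the residual variance with the split relative to exact age is (1 − R²r²)/(1 − R²).

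- R² = 0.01, r² = 0.64: ratio 1.0036.
- R² = 0.02, r² = 0.64: 0.9872/0.98 = 1.0073.
- R² = 0.05, r² = 0.60: 0.97/0.95 = 1.021.

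An analysis with 90% power using exact age would have 89.4–89.9% with the split over this range.

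Simulating the six-level outcome with an assumed odds ratio per 10 years of age of 1.2, 1.5 or 2.0 gives residual variance higher by about 0.2%, 0.7–0.9% or 2.2–2.7%. Of 2 × 507 = 1014 evaluable participants (section 9.1), that is about 2, 7–9 or 22–27.

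**3. Interaction test, analytic.** If modification is linear in age, power with the split = Φ(√r² (1.96 + z) − 1.96), where z is the normal quantile of the power with exact age. For 80% and r² = 0.64: 0.8 × 2.802 − 1.96 = 0.281, giving 61%.

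| Power, exact age | Power, split (r² 0.60–0.64) |
|---|---|
| 90% | 71–74% |
| 80% | 58–61% |
| 50% | 33–35% |

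**4. Interaction test, simulated.** A rank-sum test has no interaction term, so a linear model on the ranks stands in. Both setups use n = 1014, age 82/8, and one reading of the 7%, 10% and 20% event rates in section 9.1 that leaves 70% event-free.

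- Setup A: mean treatment odds ratio 0.64, age odds ratio 1.5 per decade, robust standard errors, 3000 runs.
- Setup B: log-odds ratio −0.46, age slope 0.03 per year, 2000 runs.

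| Change in treatment log-odds ratio | Setup | Exact age | Split |
|---|---|---|---|
| None | A | 7.0% | 6.6% |
| None | B | 6.6% | 5.3% |
| Linear, 0.20 per decade | B | 8.6% | 7.3% |
| Linear, 0.40 per decade | B | 34% | 20% |
| Linear, 0.45 per decade | A | 40% | 25% |
| Linear, 0.60 per decade | A | 65% | 41% |
| Linear, 0.60 per decade | B | 71% | 45% |
| Step of 0.5 at 80 | B | 11% | 19% |
| Step of 0.8 at 80 | B | 28% | 48% |

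The 0.64 in setup A is an odds ratio, whereas section 9.1 calls about 0.64 a log-odds ratio. The absolute powers depend on that input and on the sign of the slope: with settings like A, a slope of −0.45 gives 77% (exact) against 56% (split).

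**The case against.** The case for leaving the text alone is substantial.

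- **Adjusting for a stratification factor as randomised is standard and valid.** This stands. The point concerns efficiency, not bias.
- **The primary result cannot change.** This stands. A reader might infer that the trial's main comparison loses a third or more of its information. Section 9.2 does not support that: the rank-sum test carries no age term, and the discarded share is variance of age, not of the treatment effect.
- **Little is fixed.** This stands in part. The Koch analysis is only to be considered, and a reader should not infer that the mixed model or the secondary regressions are tied to the split, because their covariates are not listed. But the coding of age is written out for the Koch analysis and the subgroup, so an analysis plan that follows the protocol inherits it. Nothing prevents that plan from adding age in years.
- **The interaction result can reverse.** This stands. It is tempting to say that the age test is badly weakened in all cases, but a step at 80 favours the split clearly. The protocol gives no reason to expect either shape.
- **The slopes that show a large loss are steep.** This stands. With a mean log-odds ratio near −0.45, a slope of 0.45 per decade removes the whole effect ten years above the mean age. At 0.20 per decade neither test is useful.
- **The subgroup is exploratory.** This also stands: section 9.2 claims no power for it, and a prespecified cut matching a stratum is easy to read.

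**Conclusion.** The plan contains no error here, but it passes over a free improvement. The loss for the adjusted treatment effect is about 0.2–2.7% of residual variance, and the top of that range needs an odds ratio of 2.0 per decade of age.

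For the exploratory interaction, the split discards about 35–47% of age variance if age is near-normal, and about 25% if uniform. The cost is roughly 15–25 power points if modification is gradual and fairly large; little is lost if it is gentle, and the split gains if the change is a step at 80. All these figures rest on assumed age distributions, age effects and shapes of modification that the protocol does not give. The point is of minor importance.

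**What to change.** In section 9.2, and in the statistical analysis plan:

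1. Keep the below-80/80-or-over stratum indicator in the adjusted analysis and add age at randomisation in years as a continuous covariate, either linear or as a prespecified 3-knot spline.
2. For the age subgroup, prespecify a treatment-by-continuous-age interaction alongside the estimates below 80 and at 80 or over.
3. State before database lock which of the two age tests is the main one. If there is a substantive reason to expect a change at 80, the split can be named; otherwise continuous age is the natural choice.

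The cost is a sentence or two of text, with no new data, no change to randomisation and no extra participants. The small downside is that a functional form has to be prespecified and one or two degrees of freedom are used.

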5.2.2 Other study interventions

Participants pre-consented to take part in RESULT-Hip but not yet randomised

All participants enrolled in RESULT-Hip will have their haemoglobin and U&Es (urea and electrolytes) measured as per local practice. This must include a measurement preoperatively and on the first and second postoperative days at a minimum. Additional blood sampling will be at the discretion of the clinical team

Participants randomised to the study intervention (both arms)

All participants randomised to RESULT-Hip will have their haemoglobin and U&Es (urea and electrolytes) measured as per local practice. We would expect participating sites to measure Haemoglobin pre-operatively and, on the first, and second post-operative days as part of routine care.

Haemoglobin and U&Es will be measured at randomisation (baseline) and once more in days 2 - 5. Blood samples for troponin analysis (analysis to take place in Edinburgh, results not available to clinical team) will be taken at randomisation (baseline) and then twice more in days 1 to 5, ideally on the 1st and 3rd calendar days after randomisation with all samples being at least 24h apart from each other. The baseline sample should be taken as soon as possible after randomisation (on the same day and ideally within 4 hours of randomisation). ECGs will be performed at baseline and repeated once in days 2 - 5.

If it is anticipated that the participant will be discharged before Day 3, these assessments should be carried out pre-discharge.

CR007-T02 v0.5 Page **32** of **69**

IRAS 299977/308830

Version 5.0 26Jun2024

Haemoglobin will also be measured as soon as possible after every transfusion given as part of the study (ideally within 24 hours).

Additional blood sampling will be at the discretion of the clinical team unless Haemoglobin is not measured as part of routine care for 5 consecutive days. The protocols for blood sampling and measurement in each study site will be checked and clarified during site set-up.

4AT assessment will be carried out at randomisation, and then twice more in days 1 to 5, ideally on the 1st and 3rd calendar days after randomisation.

EQ-5D-5L will be measured at randomisation, or as soon as practicable after, and at days 30 +/- 7 days and at day 120 +/- 7 days.

Health services utilisation will be measured by questionnaire at 30 +/- 7 days and 120 +/- 7 days.

IRAS 299977/308830

Version 5.0 26Jun2024

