6.3 STORAGE AND ANALYSIS OF SAMPLES

Blood samples for full blood count and urea and electrolytes will be collected at randomisation, then on post randomisation day 3 (window day 2 - 5) and thereafter at the discretion of the clinical team. These will be analysed locally in routine NHS laboratories as part of routine care, and the results recorded in the CRF by the local study team.

The serum troponin measurement will be used to define the primary endpoints and secondary endpoints relating to cardiac complications. Blood will be taken for serum troponin measurement at randomisation, then twice more in days 1 to 5, ideally on the 1st and 3rd calendar days after randomisation with all samples being at least 24h apart from each other. Where possible these will be timed with routine blood sampling as part of normal clinical care. These samples will be drawn by venepuncture (or by arterial or central venous catheter if available) into serum gel. Blood should be allowed to clot for a minimum of 30 minutes then spun as soon as possible, ideally within 2 hours of sample collection. If serum gel is not available at a site, Lithium-Heparin tubes can be used, and separate instructions will be issued for sample processing.

Samples should be labelled and stored at -70C or lower until they are transported to Edinburgh for analysis. Study samples will be shipped from site and stored centrally. Frequency of shipments will be agreed on a per-site basis. Samples will be sent on dry ice to the University of Edinburgh centralised storage When ready for analysis samples will be defrosted at room temperature for 60-120min, mixed well with vortex then centrifuged. Laboratory staff will aliquot 320 μ l from the original tubes to Eppendorf tubes and set in the centrifuge basket before spinning at 3000 G, 6 degrees for 10 minutes.

The ARCHITECTSTAT high-sensitive cardiac troponin I (Troponin) assay (Abbott Laboratories, Abbott Park, IL, USA) will be used for sample analysis in this study and has a limit of detection of 1.2 ng litre⁻¹ and an inter-assay coefficient of variation of <10% at 4.7 ng litre⁻¹. The mean concentration for a healthy reference population is 1.6 (3.1) ng litre⁻¹, and the 99th percentile URL for the whole population is 26 ng litre⁻¹ (females, 16 ng litre⁻¹; 34 males, ng litre⁻¹).

Depending on time, biomarker required and availability of storage, samples will be stored for bona fide research purposes for a period 5 years after the study end date.

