Thus the assumed 30 day mortality rate is 7%, MACE at 30 days is 10%, and rate of new MINS is 20%. To detect a 30% RRR (corresponding to a log-odds-ratio of approximately 0.64) and assuming proportional odds (34) between the liberal and restrictive groups, we require a sample size of 507 participants in each arm, using a Wilcoxon-Mann-Whitney rank-sum test with a 5% two-sided significance level and 90% power. Allowing for a 10% dropout rate, we propose to recruit 563 participants per group. Total sample size 1126 participants.

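### Section 9.2 does not name baseline troponin among the covariates of its adjusted primary-outcome analysis, although the sample is planned for every participant and could add a modest amount of precision

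*Protocol*

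**What the plan says.** Section 9.2 makes an unadjusted Wilcoxon-Mann-Whitney test on the six ranks the primary analysis. It then says that Koch's non-parametric ANCOVA will also be considered because it may have more power, and lists its covariates as the randomisation strata: centre, age below or above 80, and pre-existing cardiovascular disease (CVD). Anticoagulant use is the one further candidate. Its link with CVD is to be assessed from baseline characteristics, and if that link is not strong, "then it will be included as an additional covariate in all adjusted analyses". An ordinal logistic mixed model is a secondary analysis and has no covariate list of its own. Multiple imputation is planned for missing data.

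On troponin, section 5.2.2 says that samples "will be taken at randomisation (baseline) and then twice more in days 1 to 5". They are assayed centrally and results are withheld from the clinical team. Section 6.3 states: "The serum troponin measurement will be used to define the primary endpoints and secondary endpoints relating to cardiac complications". Section 7.1 lists troponin among the baseline data. Section 9.1 gives the component rates: "Thus the assumed 30 day mortality rate is 7%, MACE at 30 days is 10%, and rate of new MINS is 20"%.

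**The concern.** The stated reason for considering an adjusted analysis is power. The covariate list nevertheless omits the baseline value of the measurement that defines the most frequent assumed component and contributes to myocardial infarction as well. The only candidate outside the strata, anticoagulant use, is admitted by its association with another covariate rather than by its expected relation to the outcome, and no cut-off is given for a strong association.

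At stake is some precision in the adjusted estimates, and some protection against chance imbalance in myocardial injury already present at entry. The data are being collected in any case.

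**Working it through.** **Inputs from the protocol**
- Section 9.1: "5% two-sided significance level and 90% power"; "we require a sample size of 507 participants in each arm"; "Allowing for a 10% dropout rate, we propose to recruit 563 participants per group".
- Section 9.1, effect: "To detect a 30% RRR (corresponding to a log-odds-ratio of approximately 0.64").
- Section 9.2: the primary test has no covariates.

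**Input not in the protocol**
- R², the share of variance in the outcome rank that baseline troponin explains beyond the covariates already in the model. Assumed range: 0 to 0.20.

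**Step 1: the plan's own figure.** The dropout step reproduces: 507/0.9 = 563.3, stated as 563. The 507 does not follow from the effect as printed. Whitehead's formula is n per arm = 6(z_α+z_β)² / [θ²(1 − Σp̄³)].
- With θ = 0.64 it gives about 231 to 328 per arm for any-event rates of 38% down to 24%.
- Reading 0.64 as an odds ratio (θ = |ln 0.64| = 0.446) gives 504 per arm for control proportions 67/20/6/7%.

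That is a separate matter. The main calculation below takes the stated 90% power as its base.

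**Step 2: effect of the covariate.** Adjustment multiplies the variance of the rank comparison by (1 − R²), so

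power = Φ[(z_α+z_β)/√(1 − R²) − z_α], with z_α = 1.960 and z_β = 1.282 (sum 3.242).

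Example: at R² = 0.10, 3.242/√0.90 = 3.417; 3.417 − 1.960 = 1.457; Φ = 92.7%. The per-arm number for an unchanged 90% is 507 × (1 − R²).

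| R² | Power from 90% base | Per arm for 90% | Power from 80% base |
|---|---|---|---|
| 0 | 90.0% | 507 | 80.0% |
| 0.02 | 90.6% | 497 | 80.8% |
| 0.05 | 91.4% | 482 | 82.0% |
| 0.10 | 92.7% | 457 | 84.0% |
| 0.15 | 94.0% | 431 | 86.0% |
| 0.20 | 95.2% | 406 | 87.9% |

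A 5-point gain from 90% needs a correlation of about 0.44, that is R² of about 0.19.

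The base matters. With 507 per arm, an odds ratio of 0.64 and control proportions 70/20/3/7%, unadjusted power is 88.1% and becomes 93.9% at R² = 0.20. With a log odds ratio of 0.64 as printed, it is 99.3% and becomes 99.8%, so almost nothing is gained.

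**Step 3: is the R² range plausible, and does the form matter?** Section 1.4.1 requires a new elevation with a rise or fall, so the baseline value may itself help decide who can have new MINS. An illustrative simulation assumed 30 to 50% of participants above the upper reference limit (URL) at baseline and 20% new MINS:

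| How 'new' is judged | R², linear log troponin | R², quintiles |
|---|---|---|
| Rise of at least 20% with peak above URL | 0.013–0.141 | 0.017–0.138 |
| Baseline at or below URL, peak above | 0.000–0.030 | 0.092–0.173 |

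Under the second definition the relation is not monotone: those already above the URL cannot become new cases. A linear term then recovers almost nothing, while categories still do. These are assumed data, useful only to show that form matters and that R² from near 0 to just under 0.20 is conceivable.

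**Step 4: which analysis gains.** The Wilcoxon-Mann-Whitney test uses no covariates, so its power is the same whatever enters the adjusted models. The table applies to Koch's ANCOVA. No figure is claimed for the ordinal model, where adjustment also changes the odds ratio being estimated.

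**The case against.** The strongest reply is that covariates beyond the strata are ordinary content for the statistical analysis plan, which section 9.2 promises before database lock and which is not shown. That plan may name troponin. This stands in part. However, section 9.2 does not leave the Koch list open: it spells out three variables and adds a rule for a fourth. Improving a stated list is a fair suggestion. For the ordinal model the reply holds: troponin is unnamed there, not excluded.

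A second reply is that the covariate is imperfect, and this stands. Section 5.2.2 has the baseline sample drawn after randomisation, on the same day with a four-hour target. The trial is open-label, and section 5.2.1 calls for the first liberal-arm unit promptly after randomisation, so some samples may follow a transfusion. Randomisation may come before surgery or as late as post-operative day 8 (section 2.3), so the value may precede or follow surgical injury. These points call for a sensitivity analysis and a flexible form; they do not rule the covariate out.

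Third, a reader might set the pilot's figure of over 60% with raised troponin (section 1.1.4) against the assumed 20% new MINS and infer that a large share enter with raised troponin. The documents do not establish this: the pilot figure is perioperative, not prevalence at randomisation. Chance imbalance is also already covered by the test's error rate.

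A reader might also take the anticoagulant rule for outcome-driven selection. It is not: it uses baseline data only. Its weakness is the missing cut-off.

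**Conclusion.** The point holds as a modest, inexpensive improvement. The protocol proposes an adjusted analysis for the sake of power and does not name a relevant baseline measurement that it already plans to take from everyone.

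A reader might infer that the trial gives away power in its primary test or falls short of its target. The documents do not support that. The stated 90% is for the unadjusted test, which is unaffected. The gain belongs to the adjusted analyses and their estimates, and reaches the primary test only if an adjusted analysis is made primary.

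The size is about 0 to 5 power points from a 90% base, for an assumed R² of 0 to 0.20. The protocol gives no correlation, so no single figure within or above that range can be claimed. The result rests on the variance-reduction formula, on the stated 90% as the base, and on a functional form that can follow a non-monotone relation.

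**What to change.** In section 9.2 or the statistical analysis plan, before any outcome data are examined by arm:

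- Name central baseline troponin I as a covariate in Koch's ANCOVA and in the ordinal mixed model. Use a pre-specified flexible form (spline or fixed categories of log troponin) rather than a single linear log term.
- Include it in the multiple-imputation model.
- State how a missing baseline value is filled in, without using treatment arm.
- Add a sensitivity analysis that omits the covariate, or that excludes baseline samples taken after a post-randomisation transfusion.
- Decide now whether anticoagulant use is in or out, in place of the rule without a cut-off.
- State plainly that the primary test is unaffected unless the adjusted analysis is made primary.

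The cost is wording and one added covariate; the assay is already planned. The drawbacks are a few missing samples and some samples that may not be strictly pre-treatment.
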